5.2.2. Packaging and Labeling

E/C/F/TAF FDC tablets are packaged in white, high density polyethylene (HDPE) bottles. Each bottle contains 30 tablets, silica gel desiccant and polyester material. Each bottle is enclosed with a white, continuous thread, child-resistant polypropylene screw cap with an induction-sealed, aluminum-faced liner.

Study drug(s) to be distributed to centers in participating countries shall be labeled to meet applicable requirements of the EU Guideline to Good Manufacturing Practice – Annex 13 (Investigational Medicinal Products), and/or other local regulations.

5.2.3. Storage and Handling

E/C/F/TAF tablets should be stored at controlled room temperature of 25 °C (77 °F); excursions are permitted between 15 °C and 30 °C (59 °F and 86 °F). Storage conditions are specified on the label. Until dispensed to the subjects, all bottles of study drugs should be stored in a securely locked area, accessible only to authorized site personnel.

To ensure the stability and proper identification, study drug should not be stored in a container other than the container in which they were supplied.

Consideration should be given to handling, preparation, and disposal through measures that minimize drug contact with the body. Appropriate precautions should be followed to avoid direct eye contact or exposure through inhalation when handling.

5.3. Dosage and Administration of E/C/F/TAF FDC

E/C/F/TAF FDC tablets will be provided by Gilead Sciences.

E/C/F/TAF FDC tablets containing 150 mg of EVG, 150 mg of COBI, 200 mg of FTC, and 10 mg of TAF will be provided to all eligible subjects at Day 1. Study drug will be administered orally at approximately the same time each day with food.

Subjects will be instructed to bring all study medication in the original container at each clinic visit for drug accountability (unless otherwise specified in the study procedures sections of this protocol).

5.4. Prior and Concomitant Medications

- Subjects receiving hormonal contraceptives should consider additional methods of contraception as concentrations of ethinyl estradiol may decrease and progesterin level may increase on co-administration with study drug.
- The use of medications for the treatment of HIV, other than study drug, is prohibited.
- Subjects receiving concomitant medications that are highly dependent on CYP3A for clearance and for which elevated plasma concentrations are associated with serious adverse events should consider alternative concomitant medications.
- During the study, subjects may not receive any of the following concomitant medications:
 - Competitors of renal excretion (e.g., probenecid; high-dose non-steroidal anti-inflammatory drugs)
 - Known nephrotoxic drugs (e.g., aminoglycosides, amphotericin B, vancomycin, cidofovir, foscarnet, cisplatin and pentamidine)
- Medications listed in the following table and use of herbal/natural supplements are excluded or should be used with caution while subjects are participating in the study. Any concomitant medication requiring adjustment or discontinuation due to renal impairment or a change in renal function on study should be managed per that drug's prescribing information.

Table 5-1. Prior and Concomitant Medications

Drug Class	Agents Disallowed	Use Discouraged and To Be Used With Caution
Acid Reducing Agents Antacids		Concentration of study drug may decrease with antacids. Subjects may not take antacids (e.g., Tums, Mylanta); the ulcer medication sucralfate (Carafate); or vitamin or mineral supplements that contain calcium, iron or zinc for a minimum of 2 hours before and 2 hours after any dose of study drug.
Alpha Adrenergic Receptor Antagonists	Alfuzosin	
Analgesics		Tramadol, Propoxyphene: Concentrations may increase with study drug(s); clinical monitoring is recommended.
Antiarrhythmics		Amiodarone, Flecainide, Quinidine, Propafenone, Systemic Lidocaine, Mexiletine, Disopyramide: Concentrations may increase with study drug(s) resulting in a potential for cardiac arrhythmias; clinical and ECG monitoring is recommended.
Calcium Channel Blockers	Bepidil	Felodipine, Nifedipine, Nicardipine, Verapamil, Diltiazem, Amlodipine: Concentrations may increase with study drug(s). Clinical and ECG monitoring of subjects is recommended.
Digoxin		Digoxin: Concomitant use may result in increased levels; use with caution and with appropriate monitoring of serum digoxin levels. Digoxin therapy should be initiated at the lower dose, and the dose should be titrated to clinical response.
Antibacterials		Clarithromycin and Telithromycin: Concentrations may be altered with study drug(s); consider an alternative.
Anticoagulants		Warfarin: Concentrations may increase or decrease with study drug(s); appropriate INR (International Normalized Ratio) monitoring is recommended.
Anticonvulsants	Phenobarbital, Phenytoin, Carbamazepine, Oxcarbazepine	Ethosuximide, Divalproex, Lamotrigine: Concentrations may increase with study drug(s); clinical monitoring is recommended.

Drug Class	Agents Disallowed	Use Discouraged and To Be Used With Caution
Antidepressants		
Selective serotonin reuptake inhibitors (SSRIs): A dose reduction may be required for most drugs of this class with the exception of sertraline.
 
Tricyclics: Concentrations may increase or decrease with study drug(s). Concentration monitoring is recommended to ensure adequate clinical response.
 
Trazodone: Concomitant use with CYP3A inhibitors results in increased concentrations and adverse events; dose reduction should be considered.

Antifungals		
Ketoconazole and Itraconazole: Concomitant use with study drug may result in an increase in concentrations. Daily dose of ketoconazole and itraconazole should be restricted to 200 mg. Subjects receiving ketoconazole or itraconazole should be monitored for adequate clinical response.
 
Voriconazole: Concomitant use with study drug may result in an increase in concentrations. Clinical monitoring may be needed.

Antigout		
Colchicine: Concentrations may increase with study drug(s). Dose reductions of colchicine may be required. Should not be coadministered in patients with renal or hepatic impairment.
 
Treatment of Gout Flare:
 
0.6 mg (1 tablet) × 1 dose, followed by 0.3 mg (half tablet) 1 hour later. Treatment course may be repeated no earlier than 3 days.
 
Prophylaxis of Gout Flares:
 
If the original regimen was 0.6 mg twice a day, the regimen should be adjusted to 0.3 mg once a day. If the original regimen was 0.6 mg once a day, the regimen should be adjusted to 0.3 mg once every other day.
 
Treatment of Familial Mediterranean Fever:
 
Maximum daily dose of 0.6 mg (may be given as 0.3 mg twice a day).

Drug Class	Agents Disallowed	Use Discouraged and To Be Used With Caution
Antihistamines	Astemizole, Terfenadine	
Antimycobacterials	Rifampin, Rifapentine, Rifabutin	
β-Blockers		Metoprolol, Timolol: Clinical and ECG monitoring of subjects is recommended. A dose decrease may be needed.
Corticosteroids: Inhaled/Nasal		Concomitant use of inhaled fluticasone and study drug(s) may increase plasma concentrations of fluticasone. Use is not recommended unless the potential benefit to the subject outweighs the risks of corticosteroid side effects. Alternatives should be considered, particularly for long-term use.
Corticosteroids: Systemic		Systemic dexamethasone, a CYP3A inducer, may significantly decrease elvitegravir and cobicistat plasma concentrations, which may result in loss of therapeutic effect and development of resistance. Alternative corticosteroids should be considered. Use of Prednisone as a steroid burst (≤ 1 week of use) should be monitored appropriately.
Endothelin Receptor Antagonists		Bosentan: Coadministration may lead to decreased elvitegravir exposures and loss of therapeutic effect and development of resistance. Alternative endothelin receptor antagonists may be considered.
Ergot Derivatives	Ergotamine, Ergonovine Dihydroergotamine Methylethergonovine Ergometrine	
GI Motility Agents	Cisapride	
Herbal/Natural Supplements	St. John's Wort, Echinacea	
HMG-CoA Reductase Inhibitors	Simvastatin, Lovastatin	Atorvastatin: Concentrations may increase with study drug(s). Start with the lowest dose; gradual increase in dose may be tailored to clinical response. Careful monitoring for signs and symptoms of muscle weakness or myopathy, including rhabdomyolysis.
Immunosuppressants		Cyclosporine, Rapamycin, Sirolimus, Tacrolimus: Concentrations may increase with study drug(s). Therapeutic monitoring should be considered.
Inhaled Beta Agonist	Salmeterol	
Neuroleptics	Pimozide	Perphenazine, Risperidone, Thioridazine: A dose decrease may be needed.

Drug Class	Agents Disallowed	Use Discouraged and To Be Used With Caution
Opiates		
Methadone: Methadone exposures are unaffected upon coadministration with elvitegravir and cobicistat. No dose adjustment of methadone is required upon coadministration with study drug(s).
 
Meperidine (Pethidine): Dosage increase and long-term use are not recommended due to increased levels of metabolite normeperidine, which has analgesic and CNS stimulant (e.g., seizures) activities.
 
Buprenorphine: Concentrations of buprenorphine and norbuprenorphine are modestly increased and concentrations of naloxone are modestly decreased when coadministered with elvitegravir and cobicistat, with no effect on opioid pharmacodynamics. The concentration changes are not considered clinically relevant and no dose adjustment of buprenorphine/naloxone is required upon coadministration with study drug(s).

Phosphodiesterase-5 Inhibitors	Sildenafil (for PAH)	
Pulmonary Arterial Hypertension:
 
Tadalafil: Caution should be exercised, including consideration of dose reduction, when coadministered for treatment of pulmonary arterial hypertension.
 
Erectile Dysfunction:
 
Sildenafil, Vardenafil, Tadalafil: It is recommended that a single dose of Sildenafil no more than 25 mg in 48 hours, Vardenafil no more than 2.5 mg in 72 hours, or Tadalafil no more than 10 mg in 72 hours be coadministered.

Sedatives/Hypnotics	Orally administered Midazolam, Triazolam	
Buspirone, Clorazepate, Diazepam, Estazolam, Flurazepam, Zolpidem: A dose decrease may be needed for these drugs. Clinical monitoring is recommended.

- Should subjects have a need to initiate treatment with any disallowed concomitant medication, the Gilead Sciences Medical Monitor must be consulted prior to initiation of the new medication. In instances where an excluded medication is initiated prior to discussion with the Sponsor, the Investigator must notify Gilead Sciences as soon as he/she is aware of the use of the disallowed medication.

5.5. Accountability of Study Drug

The Investigator is responsible for ensuring adequate accountability of all used and unused study drug. Accountability records (Study Drug Inventory Log) will be provided to each study site in order to:

- Record the date received and the quantity of study drug bottles.
- Record the date, subject number, subject initials, the study drug bottle number dispensed.
- Record the date, quantity of used and unused study drug returned by the subject, along with the initials of the person recording the information.

The Investigator [or designee (e.g., study center pharmacist)] will acknowledge receipt of the study drugs from Gilead Sciences (or designee) after reviewing the shipment's content and condition. The Investigator (or designee) will be responsible for maintaining an accurate inventory of the dates and quantities of all study drugs received, dispensed, and returned. Subjects should be instructed to return all unused study drug to the site at their study visits.

Each dose of the study drug administered at the study center will be administered by qualified study center personnel. All doses of study drug administered to subjects in the clinic under the supervision of staff will be accurately recorded on the Study Drug Inventory Logs provided by Gilead Sciences (or on equivalent documentation maintained by the study center), which indicates the date and quantity of all doses of study drug dispensed to individual subjects. The requirements of all applicable drug dispensing laws will apply to all doses of study drugs dispensed by the Investigator (or designee).

The study drug inventory log must be available for inspection by the study monitor. Study medication supplies, including partially used or empty bottles, must be accounted for by the study monitor prior to destruction or return.

5.5.1. Study Drug Return or Disposal

The study monitor will provide instructions for return. If return is not possible, the study monitor will evaluate each study center's study drug disposal procedures and provide appropriate instruction for destruction of unused study drug. If the site has an appropriate standard operating procedure (SOP) for drug destruction as determined by Gilead Quality Assurance (QA), the site may destroy used (empty or partially empty) and unused study drug bottles in accordance with that site's approved SOP. A copy of the site's approved SOP will be obtained for central files.

If study drug is destroyed on site, the investigator must maintain accurate records for all study drug destroyed. Records must show the identification and quantity of each unit destroyed, the method of destruction, and the person who disposed of the study drug. Upon study completion, copies of the study drug accountability records must be filed at the site. Another copy will be returned to Gilead. The study monitor will review study drug bottles and associated records at periodic intervals.

6. STUDY PROCEDURES

The study procedures to be conducted for each subject enrolled in the study are presented in tabular form in [Appendix 2](#) and described in the text that follows.

Any deviation from protocol procedures should be noted in the subject's clinical chart and appropriate electronic Case Report Forms (eCRFs). In addition, the sponsor or Contract Research Organization (CRO) should be promptly notified of any protocol deviations.

6.1. Subject Enrollment and Treatment Assignment

It is the responsibility of the Investigator to ensure that the subject is eligible prior to enrollment.

Subjects who provide written consent and meet all eligibility criteria will receive elvitegravir 150 mg / cobicistat 150 mg / emtricitabine 200 mg / tenofovir alafenamide 10 mg (E/C/F/TAF), on Day 1. Please refer to Section [5.1](#) for details about enrollment and treatment assignment.

6.2. Pretreatment Assessments

6.2.1. Screening Visit

Subjects will be screened within 42 days before enrollment (Day 1) to determine eligibility for participation in the study. The following will be performed and documented at screening:

- Obtain written informed consent
- Obtain medical history, including history of HIV-1 disease-related events, cigarette smoking (current or previous smoker), diabetes, family cardiovascular history and prior medications within 30 days of the Screening Visit
- Complete physical examination (urogenital/anorectal exams will be performed at the discretion of the Investigator)
- Vital signs measurement (blood pressure, pulse, respiration rate, and temperature)
- Height and weight
- 12-lead ECG performed supine
- Urine collection for the following laboratory analyses:
 - Urinalysis and Urine chemistry

- Blood sample collection for the following laboratory analyses:
 - Serum pregnancy test (females of childbearing potential only). If the test is positive, the subject will not be enrolled.
 - FSH test is required for female subjects (age > 54 years) who have stopped menstruating for > 12 months but do not have documentation of ovarian hormonal failure.
 - Chemistry profile: alkaline phosphatase, AST, ALT, total bilirubin, direct and indirect bilirubin, total protein, albumin, bicarbonate, BUN, calcium, chloride, creatinine, glucose, potassium and sodium
 - Estimated glomerular filtration rate according to the Cockcroft-Gault formula (eGFR_{CG}) {Cockcroft et al 1976}:
 - Male:
$$\frac{(140 - \text{age in years}) \times (\text{wt in kg})}{72 \times (\text{serum creatinine in mg/dL})} = \text{CL}_{\text{cr}} \text{ (mL/min)}$$
 - Female:
$$\frac{(140 - \text{age in years}) \times (\text{wt in kg}) \times 0.85}{72 \times (\text{serum creatinine in mg/dL})} = \text{CL}_{\text{cr}} \text{ (mL/min)}$$
 - Hematology profile: complete blood count (CBC) with differential and platelet count
 - CD4+ cell count
 - Plasma HIV-1 RNA
 - Hepatitis B virus surface antigen serology (HBsAg)
 - Hepatitis C virus (HCVAb) serology (reflex HCV RNA is performed in subjects with positive HCVAb serology)
 - Whole blood sample collection for proviral genotype analysis of archived resistance
- Review of concomitant medications
- Record any serious adverse events and all adverse events related to protocol mandated procedures occurring after signing of the consent form.

Subjects meeting all of the inclusion criteria and none of the exclusion criteria will return to the clinic within 42 days after screening for the Day 1 assessments.

From the time of obtaining informed consent through the first administration of study drug, record all serious adverse events (SAEs), as well as any adverse events related to protocol-mandated procedures on the adverse events electronic case report form (eCRF). All other untoward medical occurrences observed during the screening period, including exacerbation or changes in medical history are to be captured on the medical history eCRF. See Section 7 Adverse Events and Toxicity Management for additional details.

6.2.2. Day 1 Visit

Eligible historical genotype report and subsequent proviral genotype test result for archived resistance must both be reviewed and approved by Gilead to confirm subject eligibility. Once subject's full eligibility is confirmed, the following evaluations are to be completed at the Day 1 Visit. The subject must complete all Day 1 assessments before being dispensed the study drug. Initiation of treatment with the study drug must take place within 24 hours after the Day 1 visit.

- Review of AEs and changes in concomitant medications
- Complete physical examination (urogenital/anorectal exams will be performed at the discretion of the Investigator)
- Vital signs (blood pressure, pulse, respiration rate, and temperature), including weight
- Urine collection for the following laboratory procedures:
 - Urinalysis and urine chemistry
 - Urine pregnancy test (females of childbearing potential only). If the urine pregnancy test is positive at Day 1 visit, study drug will not be dispensed. The positive result will be confirmed with a serum pregnancy test. If the serum pregnancy test is positive, the subject will not be able to participate.
 - Urine sample storage for possible additional clinical testing
- Blood sample collection for the following laboratory analyses:
 - Chemistry profile: alkaline phosphatase, AST, ALT, total bilirubin, direct and indirect bilirubin, total protein, albumin, bicarbonate, BUN, calcium, chloride, creatinine, glucose, potassium and sodium
 - Cystatin C testing
 - Metabolic assessments: Fasting (no food or drinks, except water, at least 8 hours prior to blood collection) glucose and lipid panel (total cholesterol, HDL, direct LDL and triglycerides). If the subject has not fasted prior to the visit, the visit may proceed, but the subject must return within 72 hours in a fasted state to draw blood for the metabolic assessments.
 - Estimated GFR, according to the Cockcroft-Gault formula for creatinine clearance
 - Hematology profile: CBC with differential and platelet count
 - Plasma HIV-1 RNA

- CD4+ cell count
- Plasma sample storage for safety and virology testing

— CCI

- Questionnaires: Subject is to read questionnaire by her/himself and write/mark answers directly onto questionnaire.
 - Visual Analog Scale (VAS)
 - HIV Treatment Satisfaction Questionnaire Status (HIV-TSQs)
 - EQ-5D
 - Medical Outcome Study Short Form-36 (SF-36)
 - Functional Assessment of Chronic Illness Therapy – Fatigue (FACIT-F)
- Study drug dispensation. Study drug will be dispensed in an open-label fashion. Subjects must initiate dosing of study drug within 24 hours after the Day 1 visit.
- Subjects should be instructed to take E/C/F/TAF FDC tablets once daily with food at the same time each day. Subjects should also be counseled regarding the importance of adherence and taking their study medications at approximately the same time each day.

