5. INVESTIGATIONAL MEDICINAL PRODUCTS

5.1. Enrollment

This is an open-label, single arm study. All subjects will receive open-label E/C/F/TAF.

Subjects will be assigned a screening number at the time of consent. Investigators must consult with the Medical Monitor and receive written approval prior to re-screening subjects.

Prior to enrollment to Day 1, the historical genotype report and proviral DNA resistance test result must be reviewed and approved by Gilead and subject eligibility confirmed.

Once eligibility has been confirmed by Gilead, each subject will be assigned a unique subject number using an Interactive Web Response System (IWRS). Once a subject number has been assigned, it will not be reassigned to any other subject. The subject number assignment may be performed up to 3 days prior to the in-clinic Day 1 visit provided that all screening procedures have been completed and subject eligibility has been confirmed.

Eligibility and all Day 1 visit tests and procedures must be completed prior to the administration of the first dose of study drug.

The IWRS will assign open-label study drug bottle numbers at each study visit. Study drug will be dispensed to the subjects in an open-label fashion. Initiation of treatment with the study drug must take place within 24 hours after the Day 1 visit.

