### 3.7. Analysis Visit Windows

#### 3.7.1. Definition of Study Day

**Study Day 1** is defined as the day when the first dose of study drug (ie, E/C/F/TAF) was taken, as recorded on the Study Drug Administration eCRF form.

**Study Days** are calculated relative to Study Day 1. For events that occurred on or after Study Day 1 date, study days are calculated as (visit date minus date of the first dose plus 1). For events that occurred prior to Study Day 1, study days are calculated as (visit date minus date of the first dose).

**Last Dose Date** is the latest nonmissing end date of study drug (E/C/F/TAF) recorded on the Study Drug Administration eCRF form with “Study Drug Permanently Withdrawn” box checked for subjects who prematurely discontinued study drug or who completed study drug according to Study Drug Completion eCRF.

If the date of last dose is missing (eg, only year of last dose is known or completely missing due to lost to follow-up) for subjects who prematurely discontinued study drug, or for subjects who completed study drug, the latest of nonmissing study drug start dates and end dates, the clinic visit dates, and the laboratory visit dates excluding the date of 30-day follow-up visit will be used to impute the last dose date. For other partial missing last dose date, please see SAP [Appendix 5](#) for details.

**Last Study Date** is the latest of nonmissing study drug start dates and end dates, the clinic visit dates, and the laboratory visit dates including the 30-day follow-up visit date for subjects who prematurely discontinued study or who completed study according to Study Completion eCRF.

**Baseline Value** for HIV-1 RNA, CD4+ cell count, CD4%, hematology, chemistry, urinalysis and urine chemistry laboratory tests, fasting glucose and lipid panels, eGFRCG, cystatin C testing, vital signs and weight, safety electrocardiogram (ECG), Visual Analogue Scale (VAS) Adherence Questionnaire, Medical Outcome Study Short Form-36 Questionnaire (SF-36), HIV Treatment Satisfaction Questionnaire (HIVTSQ) (Status at Day 1 only), Functional Assessment of Chronic Illness Therapy – Fatigue (FACIT-F), and EQ-5D is defined as the last nonmissing value obtained on or prior to Study Day 1.

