**Table 3-3. Analysis Visit Windows for Fasting Glucose, Lipid Panels, EQ-5D, SF-36, and FACIT-F**

Nominal Visit	Nominal Day	Lower Limit	Upper Limit
Baseline	1	(none)	1
Week 24	168	2	252
Week 48	336	253	420

Lipid panel includes total cholesterol, HDL, direct LDL and triglycerides.

The analysis windows for ECG are provided in [Table 3-4](#).

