#### 7.2.2.1. Treatment-Emergent Laboratory Abnormalities

Treatment-emergent laboratory abnormalities are defined as values that increase at least one toxicity grade from baseline at any time post-baseline up to and including the date of last dose of study drug plus 30 days for subjects who permanently discontinued study drug. If the relevant baseline laboratory data are missing, then any abnormality of at least Grade 1 will be considered treatment emergent.

For serum glucose, fasting glucose and nonfasting glucose are graded based on different grading criteria as specified in the protocol. Treatment-emergent laboratory abnormalities will be summarized for fasting glucose. Since nonfasting glucose was not assessed at baseline, the maximum postbaseline grade instead of treatment-emergent laboratory abnormalities will be summarized.

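### A Day 1 fasting redraw dated after the first dose is handled as post-baseline, so fasting lipid (and usually glucose) abnormalities present before the switch are counted as treatment-emergent

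*Protocol*

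**What the plan says.** **Order of events on Day 1.** Protocol 5.1 states: "Eligibility and all Day 1 visit tests and procedures must be completed prior to the administration of the first dose of study drug". Protocol 6.2.2 adds "The subject must complete all Day 1 assessments before being dispensed the study drug" and "Initiation of treatment with the study drug must take place within 24 hours after the Day 1 visit". For a subject who has not fasted, 6.2.2 also says that "the visit may proceed, but the subject must return within 72 hours in a fasted state to draw blood for the metabolic assessments". Protocol Appendix 2 (footnote i) and SAP Appendix 1 repeat this allowance.

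**Baseline and windows.** In SAP 3.7.1, Study Day 1 "is defined as the day when the first dose of study drug (ie, E/C/F/TAF) was taken". The baseline value, with fasting glucose and lipid panels named in the list, "is defined as the last nonmissing value obtained on or prior to Study Day 1". SAP Table 3-3 ("Analysis Visit Windows for Fasting Glucose, Lipid Panels, EQ-5D, SF-36, and FACIT-F") ends the baseline window on Day 1 and runs Week 24 from Day 2 to Day 252.

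**Missing baseline.** SAP 7.2.2.1: "If the relevant baseline laboratory data are missing, then any abnormality of at least Grade 1 will be considered treatment emergent". Protocol 8.5.3 has the same rule. SAP Appendix 5, item 24, brings every post-baseline graded result into the grade summaries, whether or not it belongs to a summarized visit.

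**The concern.** The 72-hour allowance is also used at Weeks 24 and 48, where it does no harm because no first-dose deadline is running. On Day 1 it reaches past the 24-hour dosing limit. A site can follow the allowance, draw the fasting sample on the second or third day after the visit, and by then the subject has started study drug.

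The SAP has no rule for such a sample. It was collected to be the baseline, but by its date it is the first post-baseline record. An LDL or cholesterol abnormality that the subject had on the old regimen is then reported as having emerged on E/C/F/TAF. The misclassification goes one way only, and a single-arm study has no control group in which the same error would show. Safety and tolerability are a secondary objective, and fasting lipids and glucose are the parameters that SAP 7.2.1 names for its plots of change from baseline.

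**Working it through.** No power or interval figure in the plan bears on this point. The check applies the SAP's own date rules to every permitted combination of days.

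**Inputs.** Visit on calendar day 0. First dose on day 0 or +1 (within 24 hours, Protocol 6.2.2). Fasting redraw on a later day, +1 to +3 (within 72 hours, Protocol 6.2.2). Study day = draw date − first-dose date + 1 (SAP 3.7.1). Baseline if study day ≤ 1; Week 24 if study day is 2 to 252 (SAP Table 3-3).

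| First dose | Redraw | Study day | SAP window |
|---|---|---|---|
| day 0 | day +1 | 1 − 0 + 1 = 2 | Week 24 |
| day 0 | day +2 | 2 − 0 + 1 = 3 | Week 24 |
| day 0 | day +3 | 3 − 0 + 1 = 4 | Week 24 |
| day +1 | day +1 | 1 − 1 + 1 = 1 | Baseline |
| day +1 | day +2 | 2 − 1 + 1 = 2 | Week 24 |
| day +1 | day +3 | 3 − 1 + 1 = 3 | Week 24 |

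Five of the six combinations lose the baseline. This is a count of scenarios, not a probability. A redraw later on day 0 falls on or before the first-dose date in either case and is kept.

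**Is there a substitute baseline?**
- Lipids: no. Metabolic assessments are not scheduled at Screening (Protocol 6.2.1, Appendix 2). SAP 7.2.1.1 summarizes fasting values only, and SAP 7.2.2 does not grade nonfasting lipids.
- Glucose: only by chance. The Screening chemistry profile includes glucose but does not require fasting, so it serves only if that sample was recorded as fasting.

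**What follows for an affected subject.**
- Fasting values that reach a grade count as treatment-emergent. In Protocol Appendix 4, grading of adults starts at LDL 130 mg/dL, total cholesterol 200 mg/dL and fasting glucose 110 mg/dL (all Grade 1), and at triglycerides 500 mg/dL (Grade 2). HDL has no grade.
- With no baseline, the subject has no fasting change from baseline. For lipids the subject also drops out of the sensitivity analysis in SAP 7.2.1.1, which needs both baseline and Week 48 values.
- In by-visit summaries the record nearest Day 168 is chosen (SAP 3.7.3). The Day 2 to 4 value therefore stands as Week 24 only if the subject has no closer record in the window.

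**Size.** The documents give no share of unfasted Day 1 visits. Assuming 10% to 20% of the 64 subjects in SAP 1.3: 0.10 × 64 = 6.4 and 0.20 × 64 = 12.8, so about 6 to 13 arrive unfasted. This is an upper bound on baselines lost, because it supposes that every one of them is redrawn after the first-dose date. One false count is 1/64 = 1.6 percentage points. SAP 7.2.2.2 uses subjects with non-missing post-baseline values as denominator, so the figure is slightly larger if any are missing.

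**The case against.** The strongest reply is that the 72 hours are a limit and not an appointment. A subject can return fasted the next morning, give the sample, and then receive and start study drug within 24 hours of the visit, which meets every rule. That stands. A reader might infer that an unfasted subject can never comply, or that every unfasted subject loses the baseline, and the documents support neither. The SAP works by date, so even a sample taken after the dose but on the same day is kept as baseline.

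Secondly, the missing-baseline rule is deliberate. It appears in both documents and errs toward reporting too much. That is a fair defence where a baseline was never obtained. It is weaker here, because a fasting sample was collected within days of the switch and is itself entered as a post-switch finding. The laboratory listings would let a careful reader trace a Day 2 to 4 sample, but the summary tables would not show it.

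Thirdly, not every such count is false: a subject whose grade truly rises on treatment would be counted anyway. This also stands and lowers the effect further below the upper bound.

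Lastly, calling a sample taken on study drug a baseline gives up the pre-dose principle. That is a real cost, which flagging makes visible but does not remove.

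**Conclusion.** The point holds for one case: a Day 1 fasting redraw dated after the first dose. For that case the protocol's timing rules conflict, and the SAP, followed exactly, gives a wrong classification for fasting lipids, and for glucose unless a Screening value was recorded as fasting.

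The effect is limited to descriptive safety summaries: treatment-emergent grades, fasting change from baseline and the lipid sensitivity analysis. At most 6 to 13 of 64 subjects would be affected under the assumed 10% to 20% unfasted rate, with about 1.6 percentage points for each false count. A reader might take this to reach the efficacy results. It does not: Week 12 pure virologic response rests on HIV-1 RNA, which needs no fasting sample. The point should be corrected because the error goes in one direction and the correction needs no new data.

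**What to change.** **Protocol.** Reconcile 5.1, 6.2.2 (including its dispensing and dosing instructions) and Appendix 2 footnote i, together with the copy in SAP Appendix 1, on the order of fasting redraw, dispensing and first dose. Which order should apply is for the sponsor to decide; this review does not propose one.

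**SAP.** In 3.7.1, Table 3-3 and 7.2.2.1:
- identify the Day 1 fasting redraw by its nominal visit (drawn within 72 hours of the Day 1 visit), not by a fixed study day, since the same redraw has a different study day depending on when the first dose was taken;
- exclude it from the Week 24 window and from post-baseline records for treatment-emergent grading;
- use it as baseline, flagged and footnoted, when no earlier fasting value exists.

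**Cost.** One protocol clarification and a few SAP sentences. If the SAP is already final, its Section 1 provides for documenting the change in the clinical study report. The downside is that a few baselines would follow one to three days of study drug, so the footnote should give their number.
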